6.8 Protocol Schedule of Events

Study Activity	Screen/ Baseline	RP	POD 2	Wk 1	Wk 12	Mo 6 ²	Mo 9 ²	Mo 12 ²	Mo 18 ²
Visit number	1	2 Day 0	3	4	5	6	7	8	9
Allowable Visit Window from RP				+21d	+/- 14d	+/- 14d	+/- 14d	+/- 14d	+/- 14d
Consent	X								
Medical History	X								
Concomitant Meds	X			X	X	X	X	X	X
Eligibility Review	X								
Physical exam ³	X		X	X	X				
Vital signs ^{2,3}	X		X	X	X				
Questionnaires ^{1,4}	X			X	X	X	X	X	X

CBC w/diff, platelets	X		X						
Serum PSA ⁴	X				X	X	X	X	X
PRP topical application		X							
Adverse events evaluation		X	X	X	X	X	X	X	X

¹ SHIM and EPIC

7 Statistical Plan

7.1 Sample Size Determination

For the proposed trial, a sample of 20 subjects is proposed. This sample will permit a statistical description of that is required for the primary and secondary objectives. Use of 20 subjects is in the range normally enrolled for trials of this nature.

7.2 Statistical Methods

Descriptive Statistics

Univariate descriptive statistics and frequency distributions will be calculated, as appropriate for all variables. Baseline values for demographic, clinical, and outcome variables (primary and secondary) will be tabulated. Temporal trends in recovery of erectile function and urinary continence will be assessed. Normal sexual function will be defined as a Sexual Health Inventory for Men score of >19. Normal urinary continence will be defined as a response of "none" on question 5 of the Expanded Prostate Cancer Index Composite.

Handling of Missing Data

Subjects that miss follow-up appointments where data is gathered will be contacted to forward missing data records.

Multiplicity

Not applicable

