4.1 Inclusion Criteria

The study involves men newly diagnosed with prostatic adenocarcinoma that are selecting RP for treatment. The men identified for the study would be from the outpatient clinic setting and all men would be able to give appropriate informed consent.

The following are inclusion criteria for the study:

- Newly diagnosed, clinically localized prostatic adenocarcinoma
- Age 50 60 years
- Male gender
- Normal preoperative sexual function (as defined by Sexual Health Inventory for Men questionnaire score > 19; see attachment)

• Normal urinary continence (as defined by Expanded Prostate Cancer Index Composite, question 5, response = none, see attachment)Regular sexual partner

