4.2 Exclusion Criteria

- Unable or unwilling to provide informed consent
- Vulnerable study populations
- Active systemic infection
- Diabetes Mellitus diagnosis
- Preexisting ED or urinary incontinence
- Metastatic or locally advanced prostatic adenocarcinoma on preoperative evaluation
- Men found grossly or pathologically to have locally advanced or metastatic disease at the time of RP
- An estimated blood loss of >750 mL at the time of RP
- Treatment prior to surgery with any form of hormones, antiandrogens or androgen deprivation therapy
- Use of an antidepressant, beta blocker or ED medication at the time of study
- Screening Men without a regular sexual partner
- Use of aspirin or heparin 2 weeks before RP
- Need for use of aspirin or heparin for 2 weeks or more after RP.

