5.6 Prior and Concomitant Therapy

The following concomitant medicines are not permitted during the study:

- Any type of androgen deprivation therapy
- Aspirin and heparin for 2 weeks before or 2 weeks after the date of PRP application
- Use of an antidepressant, beta blocker or ED medication at the time of study screening

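### Section 7.2 counts any SHIM score above 19 as normal sexual function whether or not the man uses ED medication, and section 5.6 does not settle whether he may use it after surgery

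*Combined protocol and SAP*

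**What the plan says.** **Outcome definition.** Section 7.2 states: "Normal sexual function will be defined as a Sexual Health Inventory for Men score of >19". It applies this to a descriptive follow-up: "Temporal trends in recovery of erectile function and urinary continence will be assessed". Neither 7.2 nor 7.3 mentions ED medication. The only general provision that could reach it is "Univariate descriptive statistics and frequency distributions will be calculated, as appropriate for all variables".

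**Entry state.** Section 4.1 requires a preoperative SHIM above 19. Section 4.2 excludes "Use of an antidepressant, beta blocker or ED medication at the time of study". In the extracted text that item breaks off, and its last word seems to have moved to the start of the next bullet. I treat this as an extraction artefact, not a fault in the plan. Men therefore start above 19 and off ED medication.

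**Later use.** Section 5.6 opens with "The following concomitant medicines are not permitted during the study", but its ED item reads "Use of an antidepressant, beta blocker or ED medication at the time of study screening". Another item under the same lead-in also carries its own time window: "Aspirin and heparin for 2 weeks before or 2 weeks after the date of PRP application".

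**Data and comparator.** The schedule in 6.8 places a medication review at every visit that has the questionnaires: screening, weeks 1 and 12, and months 6, 9, 12 and 18. Sections 3.1 and 8.6 compare the cohort with concurrent registry men who meet the same entry criteria. Neither section takes account of ED medication after surgery. Section 3.3 lists the efficacy aim as secondary and joins nerve healing with a reduction in ED.

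**The concern.** The same cutoff is used before and after surgery, but the condition attached to it may change. At baseline, a score above 19 is an off-drug state. At follow-up, section 7.2 accepts the score however it was reached. A man who passes 19 only with ED medication would be counted the same as one who has regained function without it.

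This bears on what the efficacy result can mean. SHIM above 19 regardless of medication is a legitimate description of ED. It cannot by itself support the nerve-healing half of the objective. The registry comparison has the same weakness: if trial and registry men use ED medication at different rates, a difference could appear or disappear for that reason alone.

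**Working it through.** The plan states no recovery rate or ED medication rate, so there is no figure to reproduce. The check has four steps.

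**1. The two readings of section 5.6.**
- If the ED item's reference to screening governs, use after surgery is open, and drug-assisted scores enter the rate directly.
- If the lead-in governs, such scores arise only through deviations. Section 7.2 does not say how to count them.

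The gap in 7.2 exists under both readings, but it matters less under the second.

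**2. Weight of one man.** The planned cohort is 20 (section 7.1), so one man is 1/20 = 5 percentage points. If fewer men have a SHIM at a visit, one man weighs more.

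**3. Excess of the planned rate over unassisted recovery.** All inputs are my assumptions:
- p, the share of men exceeding 19 without the drug: 20%, 30%, 40%
- u, the share of the other men using ED medication: 25%, 50%, 75%
- r, the share of those users passing 19 only because of it: 20%, 30%, 40%, with r = 0 considered separately

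Excess = (1 − p) × u × r.

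| Case | Calculation | Excess | Men of 20 |
|---|---|---|---|
| No user passes 19 because of the drug | r = 0 | 0 points | 0 |
| Lowest with r above 0 | 0.60 × 0.25 × 0.20 | 3 points | 0.6 |
| Middle | 0.70 × 0.50 × 0.30 | 10.5 points | 2.1 |
| Highest | 0.80 × 0.75 × 0.40 | 24 points | 4.8 |

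Over the 27 combinations with r above 0, the median is 9 points and 2 of 27 reach 20 points. In the middle case the planned rate is 30% + 10.5% = 40.5%, against 30% unassisted.

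For scale, the exact 95% interval for 6/20 (30%) is 11.9% to 54.3%, a width of 54.3 − 11.9 = 42.4 points. Sampling error is larger than any excess in the table.

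**4. Registry comparison.** On the any-use definition, the observed difference equals the unassisted difference plus (trial excess − registry excess). As an assumed example, take p = 30% and r = 30% in both groups, with use of 75% in one and 25% in the other. The spurious difference is 0.70 × 0.30 × (0.75 − 0.25) = 10.5 points. Its sign depends on which group uses more.

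**The case against.** The strongest reply has four parts.

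- **The root is section 5.6.** If its lead-in governs, the problem nearly disappears. This stands in part: the effect depends on which reading applies. Even then, 7.2 has no rule for deviations.
- **The information is already planned.** Medications are reviewed at every questionnaire visit, and all variables get descriptive statistics. A man who entered off ED medication and later starts it has a change that the remote contacts from month 6 are meant to pick up. That is true, and it makes the remedy cheap. But the planned statistics are univariate, so a table of use alone would not show which men above 19 were users. SHIM and EPIC are listed only by title among the attachments, so I cannot check whether either asks about medication.
- **The sizes are assumed.** This stands. Raising r to 60% moves the top of the range to 0.80 × 0.75 × 0.60 = 36 points. The figures illustrate and do not estimate.
- **The endpoint is secondary and descriptive.** This stands too. There is no test or threshold to invalidate, and the primary safety objective is untouched.

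A reader might go further and infer that the plan will overstate recovery, or that it permits ED medication after surgery. The documents support neither. They do not show that any man will use it or will pass 19 because of it, and 5.6 does not settle whether he may. Nor do they show that the any-use rate is invalid, since it measures ED as experienced.

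**Conclusion.** The point holds in a limited form. As written, section 7.2 can count drug-assisted function as recovered function, and the plan has no split that would reveal it. The true size cannot be derived from the documents. It is 5 points per affected man in a cohort of 20. Under the stated assumptions it is 0 to about 24 points, and 0 if no user passes 19 because of the drug.

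Within the trial cohort the direction is upward if the rate is read as unassisted recovery. In the registry comparison it can go either way. The consequence is confined to interpreting a secondary, descriptive efficacy endpoint. An unassisted rate would come closer to the nerve-healing aim, but it would not isolate nerve healing, because section 1.1 itself describes ED after this surgery as having several causes. The change is worth making before results are seen, so that the definition is not chosen afterwards. My confidence is moderate, because the effect depends on the unresolved text of 5.6.

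**What to change.** In section 7.2, report at each visit, among men with a SHIM at that visit:

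1. SHIM above 19 with no ED medication recorded at that visit.
2. SHIM above 19 regardless of ED medication.

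Tabulate ED medication use by visit from the review already scheduled in 6.8. Count men with unknown medication status in the numerator of rate (2) only.

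Label both rates. Rate (1) is a conservative estimate of unassisted recovery only if medication use is fully reported; unreported use would put assisted men into it. Rate (2) includes drug-assisted function. Neither isolates nerve healing, and neither bounds the whole-cohort rate if SHIM scores are missing.

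For registry men, apply both definitions if ED medication is recorded. Otherwise compare only rate (2), and state that unequal use could explain a difference in either direction.

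Sections 5.6 and 4.2 must be reconciled on the period that the ED medication restriction covers. This review takes no position on which rule applies.

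**Cost.** The trial arm needs new wording and slightly more analysis, with no new visits or patients. Rate (1) gives a lower headline figure because it counts users who would exceed 19 anyway as not recovered. That shortfall is p × v, where v is the share of such men who use medication. With p of 20% to 40% and v assumed at 0 to 50%, it runs from 0 to 0.40 × 0.50 = 20 points. It belongs to the proposed rate and should not be added to the plan's excess. Registry men may need record abstraction, because section 3.1 describes only oncologic and questionnaire data for them.

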7.3 Subject Population(s) for Analysis

Data from all subjects consented for the study and completing postoperative visits will be evaluated.

² Vitals will be abstracted from the medical record for visit 3, post-operative day 2

³ Week 1 and week 12 visits may be done on-site or via telephone interview or email. Physical exam and vitals will be performed for these visits if participant is able to return to Mayo Clinic. Outside records for physical exam and vitals will be requested if visits are done remotely.

⁴ The 6, 9, 12 and 18 Month visits may be done remotely via telephone interview or email. Completed SHIM/EPIC Questionnaires may be returned to study site by mail, email or fax. PSA testing: A local clinic may be used for venipuncture, using mail in lab kit for sample return to Mayo Clinic. PSA testing window for week 12 and 6, 9, 12, 18 month visit is +/- 21d

8 Safety and Adverse Events

8.1 Definitions

Unanticipated Problems Involving Risk to Subjects or Others (UPIRTSO)

Any unanticipated problem or adverse event that meets the following three criteria:

- Serious: Serious problems or events that results in significant harm, (which may be physical, psychological, financial, social, economic, or legal) or increased risk for the subject or others (including individuals who are not research subjects). These include: (1) death; (2) life threatening adverse experience; (3) hospitalization inpatient, new, or prolonged; (4) disability/incapacity persistent or significant; (5) birth defect/anomaly; (6) breach of confidentiality and (7) other problems, events, or new information (i.e. publications, DSMB reports, interim findings, product labeling change) that in the opinion of the local investigator may adversely affect the rights, safety, or welfare of the subjects or others, or substantially compromise the research data, **AND**
- Unanticipated: (i.e. unexpected) problems or events are those that are not already described as potential risks in the protocol, consent document, not listed in the IB, or not part of an underlying disease. A problem or event is "unanticipated" when it was unforeseeable at the time of its occurrence. A problem or event is "unanticipated" when it occurs at an increased frequency or at an increased severity than expected, AND
- Related: A problem or event is "related" if it is possibly related to the research procedures.

Adverse Event

An untoward or undesirable experience associated with the use of a medical product (i.e. drug, device, biologic) in a patient or research subject.

Serious Adverse Event

Adverse events are classified as serious or non-serious. Serious problems/events can be well defined and include;

- death
- life threatening adverse experience
- hospitalization
- inpatient, new, or prolonged; disability/incapacity
- persistent or significant birth defect/anomaly

and/or per protocol may be problems/events that in the opinion of the sponsor-investigator may have adversely affected the rights, safety, or welfare of the subjects or others, or substantially compromised the research data.

All adverse events that do not meet any of the criteria for serious, should be regarded as **non-serious adverse events**.

Adverse Event Reporting Period

For this study, the study treatment follow-up period is defined as 18 months following the topical application of PRP at the time of RP.

Preexisting Condition

A preexisting condition is one that is present at the start of the study. A preexisting condition should be recorded as an adverse event if the frequency, intensity, or the character of the condition worsens during the study period.

General Physical Examination Findings

At screening, any clinically significant abnormality should be recorded as a preexisting condition. At the end of the study, any new clinically significant findings/abnormalities that meet the definition of an AE must also be recorded and documented as an AE.

Post-study Adverse Event

All unresolved AEs should be followed by the sponsor-investigator until the events are resolved, the subject is lost to follow-up, or the AE is otherwise explained. At the last scheduled visit, the sponsor-investigator should instruct each subject to report, to the sponsor-investigator, any subsequent event(s) that the subject, or the subject's personal physician, believes might reasonably be related to participation in this study.

Abnormal Laboratory Values

A clinical laboratory abnormality should be documented as an AE if the serum hemoglobin on postoperative day 2 is <8 g/dL. If hemoglobin level is considered an AE, then patient should have hemoglobin monitored and if there is a downward trend or if clinical symptoms are associated with the value then blood transfusion should be considered.

Hospitalization, Prolonged Hospitalization or Surgery

Any AE that results in rehospitalization or prolonged hospitalization (greater than 1 week) should be documented and reported as a serious AE unless specifically instructed otherwise in this protocol. Any condition requiring surgery should be documented as an AE if the condition meets the criteria for an AE.

Neither the condition, hospitalization, prolonged hospitalization, nor surgery are reported as an AE in the following circumstances:

- The planned hospitalization for RP.
- The prolonged hospitalization for diagnosis not related specifically to RP.
- Surgical procedure not related to RP.

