1.5 Dose Rationale and Risk/Benefits

The PRP sample will be prepared in the operating room from a sample of whole blood while the patient is undergoing RP. The PRP sample will be prepared by trained personnel from the Mayo Clinic Division of Transfusion Medicine using a commercially available, FDA-cleared, platelet concentration device in accordance with the manufacturer's instructions ((510K# BK110046; Angel® Concentrated Platelet Rich Plasma [cPRP] System, Cytomedix, Inc., Gaithersburg, MD USA). The Division of Transfusion Medicine has developed a detailed SOP that all staff using the Angel® system must follow in order to operate the Angel® device (http://mayoweb.mayo.edu/txmed-docs/documents/002696.pdf).

At the present time, the Angel® device is used in routine clinical use in the department of orthopedics and physical medicine and rehabilitation at Mayo Clinic. The Angel® system yields platelet concentrations of approximately 1,000,000 platelets/ mL of plasma. This dose of PRP has been demonstrated to have clinical efficacy and safety for topical applications used in orthopedic and physical medicine and rehabilitation applications.

Clinical experience with the Angel® device has demonstrated that a sample of 180 mL of whole blood will yield approximately 10 mL of PRP. This dose would be divided equally and will permit even topical application to the NVB intra-operatively at RP. The study proposes a one-time dosage period and clinical studies to date report that the duration of action for PRP is approximately 4 hours.

Risks from study participation may be related to obtaining the whole blood to produce the PRP sample or the effects of the PRP sample on the healing process after surgery. The collection of

blood would be obtained under general anesthesia required for RP using sites needed for the general anesthetic. Obtaining the whole blood could results in pain, bruising, and infection at the needle site. Obtaining a collection of blood could also have an adverse effect the patient's circulating blood volume and could result in lightheadedness or hypotension after surgery. In some instances this could require that a blood transfusion be given. Since the risk of blood transfusion for RP ranges from <1 to 5%, the independent risk of the blood collection alone requiring a postoperative blood transfusion is very low.

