4.4 Early Withdrawal of Subjects

4.4.1 When and How to Withdraw Subjects

A subject may withdraw at any time prior to RP. There are no adverse safety considerations in the study for those deciding to withdraw from the study. Subjects may choose to discontinue study participation after RP surgery and will be counted as withdrawn

A subject consenting to the study will receive PRP at the time of RP unless the surgical team decides intra-operatively to withdraw a subject from the study in the following situations:

- Estimated blood loss greater than 750 mL
- Evidence of disease grossly and/or pathologically that the prostate cancer is locally advanced or metastatic

• Documentation of the reason for withdrawal will be retained in the study files.

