5.4.1 Specifics of PRP Sample Preparation

To prepare the sample, **180** mL of whole blood will be obtained from the patient by venipuncture during the RP by Anesthesia personnel. The whole blood will be placed in the platelet concentration device and centrifuged following manufacturer's instructions. After final processing, the final PRP sample will consist of 10 mL of product that will be used for intraoperative application. The PRP created intra-operatively would be placed into a syringe labeled "PRP." Samples of whole blood and PRP will also be sent to the laboratory for analysis for quality control purposes, in accordance with Division of Laboratory Medicine SOP. ¹⁰

During the RP procedure, PRP will be applied to the NVB after completion of the vesicourethral anastomosis and after conventional techniques have been performed to achieve adequate hemostasis. Conventional techniques for hemostasis include the placement of surgical clips or suture as required to bleeding sites on the neurovascular bundle. No additional hemostatic products will be applied to the neurovascular bundles during the study. PRP will be applied evenly to the entire length of the NVB by mechanical transfer of product. For robotic procedures, a laparoscopic spoon instrument will be used to deliver the PRP directly to the NVB. For open procedures, delivery of PRP will occur via PRP-labelled syringe. After application of PRP, the surgical team will then complete RP in standard fashion.

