6.1 Visit 1; Screening and Baseline

Potential study subjects will be identified by study staff, will be provided ample time to review the informed consent document, discuss the study procedures and contents of the ICF, have all questions answered, have their medical history reviewed, vitals taken, and a physical examination performed. The baseline quality of life assessments with Sexual Health Inventory for Men and the Expanded Prostate Cancer Index Composite will be completed by the subject at this visit, if not done earlier. Baseline CBC with differential and platelet count and serum PSA samples will be obtained. If a PSA and CBC with differential and platelet count have not been performed during clinic visits at Mayo Clinic within the year prior to the screening visit and the subject has scheduled clinical labs before the screening visit, an order will be placed for the baseline PSA and CBC with differential and platelet count to ensure there is proper record of test result in the Mayo Clinic medical record. If a PSA and CBC with differential and platelet count have been performed outside of Mayo Clinic within the year prior to the screening visit and the subject does not have scheduled clinical labs before the screening visit, outside results may be used to satisfy this study visit with copies retained in study files. The study coordinator will confirm the contact information of the outside laboratory facility at the time of the screening visit and will request outside laboratory results if not already available in the Mayo Clinic medical record. However, all study eligibility requirements; including a review of current medical conditions and medications as well as written informed consent must be documented by study staff and reviewed for acceptability by an Investigator prior to enrolling the subject into the Documentation of any subjects who were consented but subsequently failed the screening requirements, including the reason for screen failure, will be retained in study files. A screening/enrollment log will be maintained.

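### A day-2 haemoglobin below 8 g/dL is the only numerical laboratory AE criterion, so zero flags would be weak reassurance about the 180 mL draw unless transfusions and haemoglobin change are also reported

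*Combined protocol and SAP*

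**What the plan says.** **Risk of the draw.** Section 1.5 states that "a sample of 180 mL of whole blood will yield approximately 10 mL of PRP". It says that taking this blood could affect circulating volume and lead to light-headedness or hypotension, and adds: "In some instances this could require that a blood transfusion be given". It then gives a background figure ("Since the risk of blood transfusion for RP ranges from <1 to 5" per cent) and judges the draw's own contribution to be very low.

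**Laboratory AE rule.** Section 8.1, Abnormal Laboratory Values, has one numerical criterion: "A clinical laboratory abnormality should be documented as an AE if the serum hemoglobin on postoperative day 2 is <8 g/dL". A flagged value leads to haemoglobin monitoring and, in stated circumstances, to considering transfusion. Day 2 is the only scheduled post-operative blood count (sections 6.3 and 6.8).

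**Blood-loss limit.** Section 4.2 excludes for "An estimated blood loss of >750 mL at the time of RP", and section 4.4.1 makes "Estimated blood loss greater than 750 mL" a ground for intra-operative withdrawal. Section 4.4.2 leaves withdrawn men's data out of the analysis. The plan does not say whether the 180 mL counts towards the 750 mL.

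**Baseline.** Section 6.1 lets tests that "have been performed outside of Mayo Clinic within the year prior to the screening visit" serve as baseline when no clinical labs are scheduled before that visit. It sets no limit on the time from screening to surgery.

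**Other capture.** The Study Summary has need for transfusion evaluated in all patients. Section 8.2 requires all AEs to be recorded, together with clearly related abnormal laboratory results, without a threshold. Section 7.2 plans descriptive statistics for all variables but names no haemoglobin change.

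**The concern.** Safety is the primary objective, and the draw is a study procedure with its own stated haematological risk. The one numerical laboratory criterion is a single absolute value on a single day, in men kept in the analysis only if operative loss stayed within 750 mL. Two things weaken a clean result on it. An ordinary haemoglobin would not normally fall that far within the limit. And a man whose haemoglobin did fall and who was transfused on day 0 or 1 may be at or above 8 g/dL by day 2. A report of no laboratory AEs in 20 men could then be read as evidence that the draw was harmless, when the criterion had little chance of showing otherwise. The natural supplement, a change from baseline, is undermined if the baseline is more than a year old by the time of surgery.

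**Working it through.** The plan gives no haemoglobin calculation, and the sample size of 20 has no formula or inputs, so there is no stated figure to reproduce.

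**Inputs from the plan:** limit 750 mL (4.2, 4.4.1); draw 180 mL (1.5, 5.4.1); cut-off 8 g/dL (8.1); n = 20 (7.1). Loss at the limit plus the draw: 750 + 180 = 930 mL.

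**Assumed, not in the plan:** blood volume (BV) 4.5-6.0 L; volume restored by day 2; starting haemoglobin (Hb) as shown.

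**Formulas:** linear, Hb × (1 − V/BV); exponential, Hb × exp(−V/BV).

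1. *Fractional fall (linear).* 930/6000 = 15.5%; 930/4500 = 20.7%.
2. *Starting value that just reaches 8.* Linear: 8/0.845 = 9.5 and 8/0.793 = 10.1 g/dL. Exponential: 9.3 and 9.8 g/dL.
3. *Result from ordinary values.* From 14 g/dL: 11.1-11.8 (linear), 11.4-12.0 (exponential). From 12 g/dL: 9.5-10.1 (linear), 9.8-10.3 (exponential).
4. *Loss needed to go from 14 to 8.* Linear: BV × (1 − 8/14) = 1.9-2.6 L. Exponential: BV × ln(14/8) = 2.5-3.4 L.
5. *Draw alone (linear).* 180/6000 = 3.0% and 180/4500 = 4.0%; times 14, a fall of 0.42-0.56 g/dL.
6. *Sensitivity to further dilution.* With another 20% on top of the exponential result, a man starting at 12 g/dL falls to 7.8-8.1 (BV 4.5-5.5 L), while one starting at 14 stays at 9.1-9.5.
7. *How little the flag moves.* Take day-2 haemoglobin as normal with mean 11 and SD 1.5 (assumed). The proportion below 8 is 2.28%, or 0.46 men in 20. Shift the mean down by 0.45 g/dL for the draw and it is 4.46%, or 0.89 in 20. With mean 12 and SD 1.0, both expected counts are 0.0.
8. *What zero means.* For 0 of 20, the one-sided 95% upper limit is 1 − 0.05^(1/20) = 13.9%.
9. *Precision of a paired change.* Half-width of the 95% interval is t(0.975, 19) × SD/√20. For an assumed SD of 1.0 it is 0.47 g/dL; for 1.5 it is 0.70 g/dL.

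**The case against.** Much of the case on the other side stands.

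- *Other routes capture harm.* A reader might infer that the laboratory safety record will look clean whatever the draw did. The documents do not support that. The Study Summary evaluates need for transfusion, which is the harm section 1.5 names; section 8.2 records all AEs and related abnormal results; sections 6.2 and 6.3 add record review at surgery and on day 2, with vital signs on day 2. What remains is that transfusion appears in neither the endpoints (3.2, 3.3), the schedule (6.8), the named analyses (7.2) nor the AE rules (8.1), so its place in the safety result is unstated.
- *The cut-off can be reached.* A reader might infer that it cannot. The 750 mL limit covers loss at operation only. Post-operative bleeding is uncapped, no minimum haemoglobin is set for entry, and step 6 shows that added dilution can be enough from 12 g/dL.
- *The age of the baseline count does not touch the flag.* The flag is an absolute value. An old count harms only a change score, which the plan does not name.
- *Nothing here isolates the draw.* In a single arm, change to day 2 mixes surgical loss, fluids and the draw, and its half-width of about 0.5-0.7 g/dL is as large as the draw's own expected effect. Section 3.1 describes the registry comparator as holding oncologic and quality-of-life data and does not mention haemoglobin.
- *The flag may be meant as a care alarm.* Section 8.1 ties it to monitoring and transfusion, and the plan never says it should measure the 180 mL effect. A rarely triggered alarm is not faulty for that reason. The point therefore concerns what its silence can be taken to show.

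**Conclusion.** The point holds in a limited form, and the remedy is cheap. Under the assumed blood volumes and simple dilution, operative loss at the limit plus the draw would not normally bring a non-anaemic man below 8 g/dL: he would have to start below about 9.3-10.1 g/dL. Transfusion before day 2 can keep a man off the flag, and the plan has no rule for that case. Zero flagged laboratory AEs would thus say little about the draw, and even a perfectly sensitive criterion with 0 of 20 leaves a true rate of up to 13.9% open. The conclusion does not extend to saying that the cut-off is wrong, that transfusions go unrecorded, or that a change score would show the effect of the draw by itself.

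**What to change.** Leave the section 8.1 flag and its care consequences as they are. Change only counting, reporting and the baseline.

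1. Reconcile the Study Summary, section 1.5 and section 8.1 so that any transfusion from the draw to discharge is counted in the safety/AE tabulation, whatever the day-2 haemoglobin.
2. In section 7.2, add the paired baseline-to-day-2 haemoglobin change with a 95% confidence interval for every man drawn. Mark values taken after a transfusion, and describe the result as the combined effect of surgery, fluids and draw. Section 5.4.1 has blood drawn during surgery, so a man may be drawn and then withdrawn for blood loss; section 4.4.2 would remove him and needs an exception for this summary.
3. In section 6.1, replace the one-year allowance for the blood count with a pre-operative count within a stated short window before surgery. Thirty days is my suggestion, not a figure from the documents. The plan says "Samples of whole blood and PRP will also be sent to the laboratory for analysis for quality control purposes", but that blood is taken during surgery and haemoglobin is not said to be measured on it, so it is no substitute for a baseline.

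The cost is wording in three sections, some repeat routine blood counts, and a few more recorded events. At the top of the plan's background transfusion range, 20 × 5% = 1 transfused man would be expected.
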